#### 6.1.2. Adjustments for Covariates

Covariates for this study include pooled site group (see [Section 6.1.6](#)) and IGA severity at baseline (mild, moderate, or severe). Subgroup analyses may be generated for the baseline covariates.

#### 6.1.3. Multiple Comparisons

No adjustments for multiple comparisons will be made for this study.

#### 6.1.4. Handling of Dropouts or Missing Data

Any subject who prematurely withdraws from the study will have their last available data assigned to an analysis window as described in [Section 6.1.5](#).

For the primary efficacy endpoint of IGA score (Phase 2b/Cohort 2 only), the primary analysis will impute missing values using a regression-based multiple imputation model. This is a three step process.

1. The first step is to understand the pattern of missingness. In order to perform the multiple imputation, a monotone missing pattern has to be achieved. For example, if there exist values for baseline, Week 8, and Week 12 visits, but missing values for the Week 2 or 4 visits, the Markov-Chain Monte-Carlo (MCMC) method will be used to impute the small amount of missing data that may be missing at the intermediate visits that is required to make the missing data pattern monotone before applying the multiple imputation algorithm. This method uses a non-informative Jeffreys prior to derive the posterior mode from the expectation-maximization (EM) algorithm as the starting values for the MCMC method. MCMC method will use seed of 74746759. The IGA score will be treated as a continuous variable for this step. To avoid values that could not be observed in practice, imputed values will be constrained to be integers in the range of 0 to 4.
  - a. The table below will determine the number of datasets to be imputed in this step. Determine the proportion of datapoints with non-monotone pattern across all visits and subjects which could be derived as a percentage of number of nonmonotone data points/total number of expected data points.

This can be determined as  $\frac{\text{number of non monotone visits}}{\text{total number of visits across all subjects}} * 100$

Non-monotone Missing Data	Number of Imputed Datasets
≤ 2%	1
> 2% to ≤ 5%	3
> 5%	10

2. Once the monotone pattern is achieved, the [next step](#) is to implement the imputation algorithm. For this, the Predictive Mean Matching method (PMM) will be used. This method is particularly helpful if the normality assumption is violated. For subjects with complete data up to a particular visit, a PMM model will be fit that includes the outcome at that visit as the dependent variable and as independent variables, IGA score outcomes at previous visits, treatment group, and pooled site group using a seed of 88734121. This process will be repeated 25 times, resulting in a total of 25 to 250 complete analysis

datasets, depending on the number of imputed monotone datasets that are required. The seed or number of imputed datasets may be changed after unblinding in case of any issues with the imputation process, and it will be documented in the CSR if any change is required.

3. For each completed dataset, compute the necessary derived variables. The dichotomous success rate (clear or almost clear) will be derived. The results obtained will be analyzed using the CMH analysis for each of the complete analysis data sets stratified by baseline IGA score and site. The results will be combined into one multiple imputation inference (odds ratio, associated CI, and *P* value) using PROC MIANALYZE as illustrated below (Ratitch 2013).

This approach to imputation should be superior to other strategies such as carrying forward the last available observation, which may yield unrealistic imputed values. Also, the use of multiple imputation avoids the problem of artificially increasing power through data imputation associated with single-imputation methods because it accounts for the uncertainty associated with the imputation. Other missing data will not be imputed, with the exception of incomplete dates as described in Section 6.1.8. For responder analyses, missing data will be treated as a nonresponse with the exception of IGA. Only observed data will be summarized using descriptive statistics.

The SAS pseudo code for the multiple imputation process is listed below:

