### Categorical Data Analysis

The primary efficacy endpoint is the rate of subjects achieving an IGA score of “Clear” or “Almost Clear” at Week 12.

The primary statistical comparisons for Cohort 2 subjects will be as follows:

- ARQ-252 cream 0.3% BID versus vehicle cream (all dose frequencies)
- ARQ-252 cream 0.3% QD versus vehicle cream (all dose frequencies)
- ARQ-252 cream 0.1% QD versus vehicle cream (all dose frequencies)
- ARQ-252 cream (all strengths and dose frequencies) versus vehicle cream (all dose frequencies)
- ARQ-252 cream 0.3% (all dose frequencies) versus vehicle cream (all dose frequencies)

The primary endpoint will be analyzed using a CMH test stratified by pooled study site group and baseline IGA category. Statistical significance will be concluded at the 10% significance level (2-sided) or less, as discussed in [Section 4.1](#). Odds ratios and 90% and 95% CIs for the odds ratios will be provided. Additionally, the 90% and 95% Wilson CIs for proportion of successes in each treatment group will be presented.

For the primary analysis, missing IGA scores will be imputed using multiple imputation as described in [Section 6.1.4](#). These imputations will result in a minimum of 25 to a maximum of 250 complete analysis datasets, depending on the number of imputed monotone datasets required. The CMH analyses will be performed separately for each of the complete analysis data sets, and the results will be combined into one multiple imputation inference (estimated treatment effect and associated CI and *P* value).

The primary efficacy analysis will be based on Cohort 2 subjects in the ITT population.

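### SAP 6.1.4 lets the imputation seed or number of datasets for the primary analysis change after unblinding on an undefined trigger, which can decide a result close to P = 0.10

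*SAP*

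**What the plan says.** For IGA in Cohort 2, SAP 6.1.4 states that "the primary analysis will impute missing values using a regression-based multiple imputation model". Two seeds are set in advance. For step 1, which makes the missing pattern monotone, "MCMC method will use seed of 74746759". For step 2, predictive mean matching (PMM), the seed is 88734121.

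The number of datasets follows a rule. On step 1 the SAP says "The table below will determine the number of datasets to be imputed in this step", and the table gives 1, 3 or 10 according to whether non-monotone missingness is at most 2%, above 2% up to 5%, or above 5%. On step 2 it says "This process will be repeated 25 times, resulting in a total of 25 to 250 complete analysis" datasets. SAP 8.1.1 repeats the total of 25 to 250.

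The text then reads "The seed or number of imputed datasets may be changed after unblinding in case of any issues with the imputation process". The only condition attached in that sentence is that a change must be recorded in the CSR.

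The step 2 pseudo-code does not carry the figure of 25. It has `nimpute=XX`, with a note that XX depends on the proportion of missing data across visits.

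**The concern.** A multiple-imputation P value carries Monte Carlo error, so it depends on the seed and on the number of datasets. Fixing both in advance removes any choice over that error. The clause reopens the choice once treatment codes are available. It does not say what an issue is, who decides, whether that person is blinded, which seed comes next, or whether the result from the original seed must be shown.

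Five primary comparisons are each read at two-sided 0.10 without multiplicity adjustment (SAP 6.1.3 and 8.1.1). All five draw on an imputation model that includes treatment group, so a new seed redraws the imputed values behind each of them. The imputed secondary IGA analyses in SAP 8.2.1 are affected in the same way.

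Other text does not close the gap. The blinded-statistician rule in SAP section 1 concerns amendments after unblinding for an interim analysis, and SAP 4.2 plans no interim efficacy analysis. The sensitivity analyses in SAP 8.1.2 use nonimputed data, so they do not test stability across seeds.

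**Working it through.** **The plan's own figure.** 25 PMM repeats × (1, 3 or 10) step 1 datasets = 25, 75 or 250. This reproduces the SAP's range of 25 to 250.

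**Simulation inputs.** From the documents: arms of 61, 61, 31, 31 and 31; planned dropout of 10% (Protocol 6.1.1); PMM on earlier visits, treatment and pooled site; CMH stratified by site group and baseline IGA; Wilson-Hilferty pooling; two-sided 0.10. Assumed, because the documents do not give them: 12 pooled sites, baseline IGA split 20/60/20%, visit-to-visit correlations, monotone dropout only, and five nearest donors in PMM. The comparison was 0.3% QD against pooled vehicle.

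Three simulated trials were kept at each dropout level because their long-run P, from 5,000 imputations, lay between 0.09 and 0.11. They are borderline by construction. Disjoint blocks of imputations on the same data then stood in for different seeds (200 blocks of 25, 20 blocks of 250).

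| Dropout | Datasets | SD of P across seeds | Range of P |
|---|---|---|---|
| 5% | 25 | 0.005 to 0.012 | about 0.07 to 0.14 |
| 10% | 25 | 0.013 to 0.015 | about 0.06 to 0.15 |
| 10% | 75 | 0.006 to 0.008 | about 0.07 to 0.13 |
| 10% | 250 | 0.003 to 0.004 | about 0.086 to 0.107 |
| 20% | 25 | 0.014 to 0.019 | about 0.06 to 0.17 |

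At 10% dropout and 25 datasets, 55% to 68% of seeds gave P below 0.10 on the same data.

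**Hand check.** With W the Wilson-Hilferty score, B its variance between imputations and m datasets, the pooled score is T = mean(W) / √(1 + (1 + 1/m)B). Treating the denominator as fixed, SD(T) ≈ √(B/m) / √(1 + (1 + 1/m)B). Near P = 0.10 (upper tail, T = 1.28, normal density 0.1755), SD(P) ≈ 0.1755 × SD(T). One of the 10% dropout trials had B = 0.151.

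- m = 25: √(0.151/25) = 0.0777; √(1 + 1.04 × 0.151) = 1.076; SD(T) = 0.072; SD(P) ≈ 0.0127 (simulated 0.0147; the formula ignores variation in the estimate of B).
- m = 250: √(0.151/250) = 0.0246; √(1 + 1.004 × 0.151) = 1.073; SD(T) = 0.0229; SD(P) ≈ 0.0040 (simulated 0.0041).

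**A clear result.** Take observed rates of 45% and 15% with 55 versus 56 subjects, the numbers in SAP 3.2. The pooled rate is (24.75 + 8.4)/111 = 0.299. Then z = 0.30 / √(0.299 × 0.701 × (1/55 + 1/56)) = 3.45, so X = z² = 11.9. W = (11.9^(1/3) − 7/9) / √(2/9) = 3.20, and 3.20/1.076 = 2.97. That is 1.69 above the threshold of 1.28, or more than 20 seed SDs of 0.072. No plausible change of seed would alter it.

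**The case against.** The strongest defence is that this is a technical contingency and not a licence to choose. The change is tied to trouble with the imputation process and to a change being required. Both seeds are published and the count follows a table, so any departure is visible and can be rerun. Protocol 6.1 requires changes to SAP methods to be described and justified in the CSR. The nonimputed ITT and PP analyses would show whether a conclusion depends on imputation.

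There is also a legitimate reason for some contingency. SAP 6.1.6 pools sites so that each pooled site has at least one subject in every treatment group, so the final site variable needs the real codes. A dry run on dummy codes cannot rule out every failure. In addition, IGA cannot be done remotely (SAP 6.2), so COVID-19 gaps may push non-monotone missingness above 2% and the total to 75 or 250, where the seed matters less.

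All of this stands, and it limits the point. It does not remove it. The trigger is still open-ended, disclosure records a choice without preventing it, and the contingency can be kept with a definition attached.

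A reader might infer that the SAP allows the primary imputation to be rerun at will until a favourable P value appears, or that pre-specification as a whole has failed. The documents support neither. The clause is conditional and disclosed, and nothing in it suggests intended misuse.

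**Conclusion.** The point holds as a gap in pre-specification that is cheap to close. When a primary P value is near 0.10 and 25 datasets are used, the seed alone can put it on either side of the threshold: about 0.06 to 0.15 at 10% dropout. At 250 datasets the range is about 0.086 to 0.107, so a larger number shrinks the problem but does not end it. Locking the seed is the essential step.

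The sizes rest on the assumed site count, baseline IGA mix, visit correlations and monotone dropout; the 5% and 20% runs show how they move. Because the simulated trials were selected to be borderline, they say nothing about how often this trial would fall near 0.10, and they give no estimate of type I error inflation. For a clear result the clause has no practical effect.

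**What to change.** In SAP 6.1.4:

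- Delete the open-ended permission. Lock both seeds and one total number of datasets before unblinding. The table depends only on missingness, so the count can be settled while blinded.
- Set the total to at least 250, already the SAP's maximum: 250 PMM repeats with one step 1 dataset, 84 with three (252 in all), 25 with ten. Align the `nimpute=XX` text in the step 2 code with this.
- Allow a change only for a defined technical failure: a program error or non-convergence, so that no valid result is produced. Only on that trigger, move to the next seed on a list ordered in advance. A list without the trigger would recreate the discretion.
- Report the original-seed result whenever that run completed.
- Test the code before lock on dummy treatment codes, recognising that this checks the program and not the final treatment-by-site data.

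The cost is SAP wording and slightly more computing time. Sample size and trial conduct are untouched.

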Power and Sample Size:	
Cohort 1 will include approximately 6 evaluable subjects, which is deemed adequate for the purpose of evaluating safety and PK prior to Cohort 2.
 
There are approximately 215 subjects planned for Cohort 2. Approximately 61 subjects will receive ARQ-252 cream 0.3% QD, approximately 61 subjects will receive ARQ-252 cream 0.3% BID, approximately 31 subjects will receive ARQ-252 cream 0.1% QD, approximately 31 subjects will receive matching vehicle cream QD, and approximately 31 subjects will receive vehicle cream BID. The randomization scheme will be 2:2:1:1:1 between these 5 treatment groups, stratified by study site and IGA at Baseline.
 
The primary statistical comparisons will be to assess the ARQ-252 cream 0.3% BID group versus the vehicle BID group, to assess the ARQ-252 cream 0.3% QD group versus the vehicle QD group, and to assess the ARQ-252 cream 0.1% QD group versus the vehicle QD group.
 
A sample size of 55 per active arm and 28 per vehicle arm will provide approximately 85% power at the 2-sided 5% significance level to detect a difference in the percent of subjects with IGA clear or almost clear at Week 12; for each ARQ-252-treated group versus vehicle group within the same daily dosing frequency, assuming an active treatment response rate of 45% and a vehicle response rate of 15%, with a two-sided $\alpha = 0.1$. This is based on a 2-group X^2 test of equal proportions (without continuity correction). With a 10% dropout rate, the sample size for the study is increased to 61 subjects per active arm and 31 subjects per vehicle arm (215 subjects total).
 
The primary statistical comparisons and evaluation of the secondary endpoints will not be adjusted for multiplicity.

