6.2 Efficacy Evaluation

6.2.1 Primary Efficacy Endpoint

The primary efficacy endpoint is the rate of subjects achieving an IGA score of ‘clear’ or ‘almost clear’ at Week 12.

The primary statistical comparisons will be to assess the ARQ-252 cream 0.3% group BID group versus the vehicle BID group, to assess the ARQ-252 cream 0.3% QD group versus the vehicle QD group, and to assess the ARQ-252 cream 0.1% QD group versus the vehicle QD group.

The primary endpoint will be analyzed using a Cochran-Mantel-Haenszel test stratified by IGA at Baseline and study site. Statistical significance will be concluded at the 2-sided 10% significance level for each of the primary comparisons. Missing scores will be imputed using multiple imputation.

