### **3.2. Sample Size and Power**

Cohort 1 will include approximately 6 evaluable subjects, which is deemed adequate for the purpose of evaluating safety and PK before Cohort 2 commences.

There are approximately 215 subjects planned for Cohort 2. The primary statistical comparisons will be to assess the ARQ-252 cream 0.3% BID group versus the vehicle BID group, to assess the ARQ-252 cream 0.3% QD group versus the vehicle QD group, and to assess the ARQ-252 cream 0.1% QD group versus the vehicle QD group. A sample size of 55 per active arm and 28 per vehicle arm will provide approximately 85% power at the 2-sided 10% significance level to detect a difference in the rate of subjects attaining an IGA score of clear or almost clear (for each ARQ-252-treated group versus vehicle group within the same daily dosing frequency), assuming an active treatment response rate of 45% and a vehicle response rate of 15%. For testing each active arm of 55 subjects versus the combined vehicle arms of 56 subjects, this sample size provides over 90% power for the comparison of the rate of subjects attaining an IGA score of clear or almost clear. This is based on a 2-group X2 test of equal proportions (without continuity correction).

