**Step 2:**

```
proc mi data=example_1 seed=88734121 nimpute=XX out=example_2;  
  class <treatment> <site>;  
  monotone regpmm(<baseline score> ..... <visit12 score>);  
  var <treatment> <site> <baseline score> ..... <visit12 score>;  
run;
```

XX will be the determined based on the proportion of missing data across visits.

**Step 3:** This step involves running CMH test stratified by baseline IGA score and site on each completed dataset and combining the results using PROC MIANALYZE.

```
proc freq data=example noprint;  
  by <imputationnumber> <visit> ;  
  tables <site> * <BL IGA> * <treatment> * <outcome> / cmh alpha=0.1;  
  output out=example_stat cmh;  
run;
```

In order to apply PROC MIANALYZE, normalizing transformations have to be applied to odds ratio. *P* values are obtained using Wilson Hilferty transformation as illustrated (Ratitch 2013).

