### 6.1.6. Pooling of Sites

Sites will be pooled for statistical analysis as follows. For analysis, sites should have a minimum of 10 randomized subjects. The smallest sites will be grouped sequentially in order of smallest to largest within each country, restricting to those sites that did not meet the minimum enrollment of 10, until each pooled site has a minimum of 10 subjects within each country with at least 1 subject in each treatment group.

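### SAP 6.1.4 Step 3 stratifies the primary CMH by site, while SAP 6.1.2, 6.1.6, 8.1.1 and the table shells use pooled site group, and the pooling is not declared as a change from the protocol

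*SAP*

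**What the plan says.** **Places that say site.**
- SAP 6.1.4, Step 3 text: the CMH analysis of each completed data set is "stratified by baseline IGA score and site".
- SAP 6.1.4, the sentence that introduces the Step 3 code: "This step involves running CMH test stratified by baseline IGA score and site on each completed dataset". The PROC FREQ TABLES statement below it crosses site with baseline IGA, and the Step 2 CLASS and VAR statements also list site.
- Protocol 6.2.1: the primary endpoint is "analyzed using a Cochran-Mantel-Haenszel test stratified by IGA at Baseline and study site".

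**Places that say pooled site group.**
- SAP 6.1.2 names pooled site group as the study covariate and refers to 6.1.6.
- SAP 6.1.6 gives the rule: "For analysis, sites should have a minimum of 10 randomized subjects". Smaller sites are combined within country until each group has that number and every arm is represented.
- SAP 6.1.4, Step 2 text, puts pooled site group in the imputation model.
- SAP 8.1.1: the primary endpoint is "analyzed using a CMH test stratified by pooled study site group and baseline IGA category".
- The footnotes of the primary table shells (for example Table 14.2.1.1.1) agree with 8.1.1.

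SAP Section 10 lists the departures from the protocol, some of them small. Site pooling is not among them.

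**The concern.** Step 3 is the operating instruction for the primary analysis. Section 8.1.1 sends the reader to 6.1.4 for the imputation, and 6.1.4 then says how to test each completed data set. A programmer who follows it gets different strata from one who follows 8.1.1, and so a different odds ratio, confidence interval and P value.

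The literal reading is a plausible one. It matches the protocol and the randomization strata. The SAP also uses study site for the individual center elsewhere: the by-site IGA success tables are keyed on site name and site ID.

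The two sets of strata are not equally usable. About 215 subjects at about 45 sites, split again by three IGA grades, leave very thin strata, and a stratum that lacks one of the two arms adds nothing to a CMH test. The strata should be settled before unblinding. The only changes that 6.1.4 provides for after unblinding are to the seed and the number of imputed data sets.

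**Working it through.** **1. The plan's own power figures.** SAP 3.2 uses an unstratified chi-square test without continuity correction, with 45% against 15%. It states "A sample size of 55 per active arm and 28 per vehicle arm will provide approximately 85% power at the 2-sided 10% significance level", and over 90% for 55 against 56 pooled vehicle. Protocol 6.2.1 confirms the level: "Statistical significance will be concluded at the 2-sided 10% significance level for each of the primary comparisons". With p̄ the weighted mean rate,

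power = Φ{[0.30 − 1.645·√(p̄(1−p̄)(1/n₁+1/n₀))] / √(0.45·0.55/n₁ + 0.15·0.85/n₀)}

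- 55 v 28: p̄ = 28.95/83 = 0.349; (0.30 − 1.645 × 0.1106)/0.0952 = 1.24; power 89.3%, not 85%.
- 55 v 56: p̄ = 33.15/111 = 0.299; (0.30 − 1.645 × 0.0869)/0.0823 = 1.91; power 97.2%, so over 90% is right.
- 28 v 56 (the 0.1% arm of 31 after 10% dropout): p̄ = 0.25; (0.30 − 1.645 × 0.1002)/0.1054 = 1.28; power 90.0%.

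The 85% is therefore a soft benchmark. The protocol synopsis even has "approximately 85% power at the 2-sided 5% significance level", which gives 80.9% for 55 v 28. None of these figures allows for stratification.

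**2. Why thin strata matter.** In stratum k, with n₁ₖ active, n₀ₖ vehicle, m₁ₖ responders, m₀ₖ non-responders, Nₖ subjects and aₖ active responders, the CMH statistic is

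[Σ(aₖ − n₁ₖm₁ₖ/Nₖ)]² / Σ[n₁ₖn₀ₖm₁ₖm₀ₖ/(Nₖ²(Nₖ−1))].

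If n₁ₖ or n₀ₖ is zero, both terms are zero, and so are the stratum's terms in the Mantel-Haenszel odds ratio. Overall there are 215/45 = 4.8 subjects per site, or 4.8/3 = 1.6 per site-by-IGA cell. The comparison of one 0.3% arm with pooled vehicle has 61 + 62 = 123 subjects, or 2.7 per site. The 0.1% comparison has 31 + 62 = 93, or 2.1 per site.

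**3. Simulation.**
- From the documents: N = 215, 2:2:1:1:1 allocation within site and IGA, about 45 sites, 45% v 15%, two-sided 0.10, and the 6.1.6 pooling rule.
- Assumed: permuted blocks of 7, baseline IGA 20/60/20 (the protocol gives only 20% caps on mild and severe), and the site-size spread, given as a coefficient of variation (CV).
- Each row has 500 runs, with a Monte Carlo error of 1–2 points. The comparator is pooled vehicle.

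| Sites, CV | Arm | One-arm strata: site | pooled | Power: site | pooled |
|---|---|---|---|---|---|
| 45, equal | 0.3% | 47.7% | 16.1% | 86.2% | 97.2% |
| 45, 0.7 | 0.3% | 39.2% | 15.3% | 88.4% | 94.2% |
| 45, 1.0 | 0.3% | 34.4% | 14.7% | 92.0% | 95.0% |
| 30, 0.7 | 0.3% | 27.6% | 14.2% | 93.0% | 96.4% |
| 45, equal | 0.1% | 59.7% | 27.0% | 60.2% | 82.6% |
| 45, 0.7 | 0.1% | 50.1% | 25.5% | 75.4% | 87.8% |
| 45, 1.0 | 0.1% | 43.5% | 23.2% | 77.4% | 82.8% |
| 30, 0.7 | 0.1% | 37.3% | 22.9% | 80.8% | 86.0% |

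The pooling rule gives about 14 groups here. In subjects, 34–48% of 123 is about 42–59 and 43–60% of 93 is about 40–56. With pooling the counts are about 17–21 (14–17%) and 21–26 (23–28%).

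**4. Sensitivity.** Letting baseline IGA shift the response odds (multipliers 1.8, 1 and 0.5, also assumed) gives 84–89% (0.3%) and 61–76% (0.1%) with site strata at 45 sites, against 94–95% and 82–85% with pooled groups. With 193 subjects, a complete-case bracket, site strata give 76–87% and 57–69%. The runs in the table have no site effect and no imputation variance.

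**The case against.** The strongest reply is that this is loose wording and the intent is clear. Section 6.1.6 is a general rule for the statistical analysis, 6.1.2 and 8.1.1 adopt it, and the shells repeat it. In Step 2 of 6.1.4 the text says pooled site group while the code writes site for the same variable, so site also serves as a placeholder there. The code is labeled pseudo-code, and the protocol describes its own methods as a summary of the SAP. Most of this stands. A reader might infer that the sponsor has settled on 45 individual sites as strata, and the documents do not support that: no place in them says individual site.

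A reader might also infer that the site reading breaks the stated power. That goes too far. The over-90% figure is an unstratified calculation for 55 against 56, so it does not describe the 31-subject 0.1% arm. For the 0.3% arms the result depends on the number and size of sites, with 92% at 45 very unequal sites and about 90–93% at 30. Nor do all comparisons lose over half of their subjects: that happens only for the 0.1% arm, and only in some scenarios. Pooling has its own cost in one-arm strata.

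The reply does not dispose of the Step 3 text. It is ordinary prose outside the code, it agrees with the protocol, and nothing in the SAP defines site as the pooled group. Section 10 is silent either way.

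**Conclusion.** The contradiction is real, and Step 3 is wrong as written. It is an inconsistency to correct, since pooled site group is very probably intended. The correction is more than clerical, because following Step 3 literally gives a weaker primary analysis. Across the runs at about 45 sites and N = 215, power against pooled vehicle is about 84–92% for the 0.3% arms and 60–77% for the 0.1% arm with site strata. With pooled groups it is about 91–97% and 78–88%.

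These sizes rest on the assumed block size, IGA mix and site-size spread, and on the planned rather than the enrolling number of sites. The conflict between the passages rests on none of them.

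**What to change.** In SAP 6.1.4, replace site with pooled site group (Section 6.1.6) in four places: the Step 3 text, the sentence that introduces the Step 3 code, the Step 2 CLASS and VAR statements, and the Step 3 TABLES statement. In Section 10, add site pooling as a declared change from the strata in protocol 6.2.1. Do both before unblinding.

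The cost is a few words and the placeholder names in the code, with no new data and no new analysis. The change does not bring the 0.1% arm to 90% power, because that arm has about 31 subjects and not the 55 assumed in SAP 3.2.
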